3.5.2. Laboratory Safety Tests

Safety laboratory tests will be performed as described in the protocol. Baseline will be defined as the last pre-dose measurement.

Appendix 2 of the protocol lists clinical laboratory tests to be performed.

3.5.3. Vital Signs

Oral temperature, pulse rate, respiratory rate, and blood pressure will be assessed at times detailed in the Schedule of Activities given in the protocol.

3.5.4. ECG Data

ECG will be collected as described in the protocol. Abnormal ECG findings (See Protocol Appendix 7) may be reported as adverse events.

3.5.5. Physical Examinations

A complete physical examination will include, at a minimum, assessments of the head, ears, eyes, nose, mouth, skin, heart and lung examinations, lymph nodes, gastrointestinal, musculoskeletal, and neurological systems. Height and weight will also be measured and recorded.

A brief physical examination will include, at a minimum, assessments of the the general appearance, the respiratory and cardiovascular systems, as well as participant reported symptoms.

3.5.6. Injection Site Reactions

Injection site reactions will be monitored for each subject from Day 1 to Day 7.

3.5.7. Other Safety Data

Additional safety data will be collected as described in the protocol and will be listed if collected in the sponsor's database.

4. ANALYSIS SETS (POPULATIONS FOR ANALYSIS)

Data for all participants will be assessed to determine if participants meet the criteria for inclusion in each analysis population prior to releasing the database and classifications will be documented per standard operating procedures.

Table 4. Analysis Sets

Population	Description
Enrolled	"Enrolled" means a participant's, or their legally authorized representative's, agreement to participate in a clinical study following completion of the informed consent process. Potential participants who are screened for the purpose of determining eligibility for the study, but do not participate in the study, are not considered enrolled.
Safety	All participants enrolled in this study who receive at least 1 dose of the study drug.
PK concentration	All participants treated who have at least 1 concentration.
PK parameter	All participants treated who have at least 1 of the PK parameters.
PD parameter	All participants treated who have at least 1 of the PD parameters.

5. GENERAL METHODOLOGY AND CONVENTIONS

5.1. Hypotheses and Decision Rules

No formal hypothesis testing will be performed.

5.2. General Methods

Descriptive analyses will be performed.

For continuous variables, the data will be summarized using the number of subjects, mean, median, standard deviation, minimum, and maximum in accordance with current Pfizer's data and reporting standards. For appropriate PK and PD parameters, geometric mean and geometric coefficient of variation (geocy%) will also be summarized.

For categorical or ordinal variables, number of subjects, numbers and percentages of subjects meeting the categorical criteria will be supplied in accordance with current Pfizer's data and reporting standards.

5.3. Methods to Manage Missing Data

For the analysis of safety endpoints, the sponsor data standard rules for imputation will be applied.

5.3.1. Concentrations Below the Limit of Quantification

In all data presentations (except listings), concentrations below the limit of quantification (BLQ) will be set to zero. (In listings BLQ values will be reported as "<LLQ", where LLQ will be replaced with the value for the lower limit of quantification). For PK calculations, BLQ will be handled by the Pfizer standard processes. For PD calculations, BLQ values will be imputed as 0.5*LOQ in calculations.

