6. ANALYSES AND SUMMARIES

6.1. Primary Endpoints (Safety Analyses)

All safety analyses will be performed on the safety population (as defined in Section 4).

Analysis of frequency, severity and causal relationship of AEs, TEAEs from Day 1 up to Day 42, and injection site reactions from Day 1 up to Day 7 will be provided. Changes from baseline in vital sign (blood pressure (BP), pulse rate, temperature and respiration rate) measurements and ECG parameters from Day 1 up to Day 28 will be summarized. Physical examination findings from Day 1 up to Day 28 will be listed. Frequency and magnitude of abnormal laboratory findings (including hematology, PT/INR, APTT, chemistry, urinalysis, fibrinogen, ATIII activity, and cTnI), ECG, BP, and pulse rate abnormalities from Day 1 up to Day 28 of potential clinical concern will be described. Safety data will be presented in tabular and/or graphical format and summarized descriptively, where appropriate, according to sponsor reporting standards.

For ECG data, the number of participants with uncorrected QT values >500 msec will be summarized. Listings of subjects with any single postdose value ≥500 msec will also be produced for QTcF. Numbers and percentages of subjects meeting the categorical criteria will be provided. All planned and unplanned measurements will be counted in these categorical summaries. All values meeting the criteria of potential clinical concern will be listed.

Seperate analysis for PT/INR, APTT, fibrinogen, ATIII activity and cTnI will include:

- Descriptive summary including n, mean, median, standard deviation, geometric mean, geometric coefficient of variation (geocv%), minimum, and maximum, will be reported from Day 1 up to Day 28.
- Listing of abnormalities.

Analysis change from baseline for PT/INR, APTT, fibrinogen, ATIII activity and cTnI will include:

• Descriptive summary including n, mean, median, standard deviation, minimum, and maximum, will be reported from Day 1 up to Day 28.

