6.2.2. Pharmacodynamic Analysis

The PD parameters from Day 1 up to Day 28 detailed in Section 3.2.2 will be listed and summarized for subjects in the PD Parameter Analysis Set (as defined in Section 4).

Separate analysis for TFPI (total and free), dPT, PF1+2, D-dimer, and thrombin generation (parameters may include lag time, peak thrombin generation, and endogenous thrombin generation potential) for subjects in the PD analysis set (as defined in Section 4) will include:

- Descriptive summaries of PD endpoints by day and nominal time post dose, where the set of statistics will include n, mean, median, standard deviation, geometric mean, geometric coefficient of variation (geocv%), minimum and maximum.
- Median pharmacodynamic endpoint time plots against sampling time.
- Mean pharmacodynamic endpoint time plots against sampling time.
- Individual pharmacodynamic endpoint time plots against sampling time.

Maximum change from baseline and area under effect curve for change from baseline PD values may be summarized if data allow.

Table 6. Other PD Parameters

Parameter	Definition	Method of Determination
Max _{Eff}	Maximum increase and decrease from baseline for free TFPI.	Observed directly from data
	Maximum increase from baseline for total TFPI, PF1+2, D-dimer, endogenous thrombin generation potential.	
	Maximum decrease from baseline for dPT, thrombin generation lag time, peak thrombin generation.	
AUEC	Area under the PD change from baseline-time profile from time zero to Day 28.	Linear/Linear trapezoidal method

The analysis of above parameters for subjects in the PD analysis set (as defined in Section 4) will include:

• Descriptive summary including n, mean, median, standard deviation, coefficient of variation (cv%), minimum, and maximum, will be reported.

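### The SAP's zero rule for values below the limit of quantification conflicts with the geometric statistics planned for PD endpoints and with its own half-LOQ rule for PD calculations

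*SAP*

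**What the plan says.** SAP 5.3.1 has three rules for BLQ results outside listings.

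- Tables and plots: "In all data presentations (except listings), concentrations below the limit of quantification (BLQ) will be set to zero".
- PK derivations: "For PK calculations, BLQ will be handled by the Pfizer standard processes".
- PD: "For PD calculations, BLQ values will be imputed as 0.5*LOQ in calculations".

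SAP 6.2.2 summarises the PD endpoints (total and free TFPI, dPT, PF1+2, D-dimer and thrombin generation) by day and nominal time, "where the set of statistics will include n, mean, median, standard deviation, geometric mean, geometric coefficient of variation (geocv%), minimum and maximum". It also plans mean, median and individual plots and, if the data allow, a maximum effect (MaxEff) and an area under the effect curve (AUEC), both based on change from baseline.

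The PK concentration summary in SAP 6.2.1.2 differs. It has no geometric statistics and it reports how many values lie above the quantification limit.

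For cardiac troponin I (cTnI), SAP 6.1 also plans a geometric mean and geometric CV. SAP 5.3 says of safety endpoints: "For the analysis of safety endpoints, the sponsor data standard rules for imputation will be applied". Those sponsor rules are not reproduced.

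**The concern.** A geometric mean and geometric CV are computed on the log scale, where a zero has no value. The zero rule suits the PK concentration table, which avoids geometric statistics, but not the PD table, which requires them. Nothing in the SAP says what to do with a zero on the log scale, or whether a PD summary statistic is a presentation (BLQ = 0) or a calculation (BLQ = 0.5 × LOQ).

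Two things are at stake. First, the programmer would have to choose, possibly after seeing the data, between reporting zero, reporting nothing, dropping the BLQ participants or substituting another value. With about 6 participants, that choice can change the reported figure materially. Second, a change read off a PD table or plot would not match the derived MaxEff or AUEC for the same participant.

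**Working it through.** The plan states no figure on this point, so there is none to reproduce.

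**Inputs.** From the SAP: the BLQ rules (5.3.1), the PD statistics (6.2.2) and n of about 6 (2.2). Not in the documents: the LOQ of any assay and the proportion of BLQ results. Both are assumed below, and values are in LOQ units.

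**Formulas.** Geometric mean = exp(mean of ln x). Geometric CV% = 100 × √(exp(s²) − 1), where s is the SD of ln x.

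**1. Zero rule.** ln 0 is minus infinity. The log formula for the geometric mean is undefined, and the product form gives 0. The SD of ln x does not exist, so the geometric CV cannot be computed by either route. One BLQ value is enough.

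**2. Illustration.** Assume six values of 1.2, 1.5, 2, 2.5, 3 and 4 LOQ, and let the lowest k be BLQ.

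| k of 6 BLQ | Zero rule | BLQ dropped: GM, CV (n) | 0.5 × LOQ: GM, CV (n) | Ratio of GMs, dropped to 0.5 × LOQ |
|---|---|---|---|---|
| 1 | GM 0 or undefined, no CV | 2.46, 39% (5) | 1.89, 84% (6) | 1.30 |
| 2 | same | 2.78, 30% (4) | 1.57, 114% (6) | 1.77 |
| 3 | same | 3.11, 24% (3) | 1.25, 134% (6) | 2.49 |

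Dropping BLQ values raises the geometric mean and shrinks the apparent spread.

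**3. General form.** Let g be the geometric mean of the quantifiable values. Dropping gives g. Substitution gives g^((6−k)/6) × 0.5^(k/6). The ratio is therefore (g/0.5)^(k/6).

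| g | k = 1 | k = 2 | k = 3 |
|---|---|---|---|
| 1.5 | 1.20 | 1.44 | 1.73 |
| 3 | 1.35 | 1.82 | 2.45 |
| 10 | 1.65 | 2.71 | 4.47 |

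**4. Table or plot against derived parameter.** With a BLQ baseline and a peak of 3 LOQ, MaxEff is 3 − 0.5 = 2.5 LOQ. The tabulated or plotted values imply 3 − 0 = 3.0 LOQ.

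**5. Arithmetic means.** The two rules differ by 0.5 × LOQ × k/6, which is 0.083, 0.167 or 0.25 LOQ for k = 1, 2 or 3.

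**6. How often it could arise.** If each result is BLQ independently with probability p, the chance of at least one BLQ among 6 at a time point is 1 − (1 − p)^6. For assumed p of 2%, 5%, 10% and 25% this is 11%, 26%, 47% and 82%.

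**7. Does another rule catch it?** SAP 5.3.2 suppresses summaries when more than half the data are missing. It sets to missing only samples not done or not taken, and values with a sampling-time deviation of concern or flagged as anomalous. A BLQ result set to zero is not among these, so it counts as data.

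**The case against.** **The half-LOQ sentence may already cover the PD tables.** SAP 5.3.2 and 5.3.3 use the language of calculation for summary statistics, so a PD geometric mean could be called a calculation. It would then be finite and agree with MaxEff and AUEC. This reading is possible, so the defect is an unresolved conflict between two sentences and not a certain failure. It is the weaker reading, however. The PK sentence in SAP 5.3.1 has the same structure. If calculations include summary statistics, the PK tables also leave the zero rule, which then governs almost nothing. Nor does this reading reach the individual PD plots, where nothing is calculated.

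**The zero rule speaks of concentrations, and SAP 6.2.2 speaks of PD endpoints.** That gives some support to a PK-only reading, but Protocol 8.6 describes the PD markers as biomarker concentration data.

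**The problem may seldom occur.** This stands. There is no LOQ or BLQ rate in the documents. Lag time and dPT are times and are unlikely to be BLQ (an assumption). SAP Table 6 looks for increases in total TFPI, PF1+2 and D-dimer, which makes post-dose BLQ results less likely. Free TFPI is analysed only if its assay is validated before the study completes. Medians, ranges, individual plots and listings are also planned.

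**A stronger reading on cTnI.** A reader might infer that zero is also imposed on cTnI, leaving a statistic attached to a primary endpoint undefined. The documents do not support this, because SAP 5.3 sends safety endpoints to sponsor rules whose content is not shown. The half-LOQ mismatch does not apply either, since cTnI is not a PD endpoint. The primary endpoint concerns abnormal findings, and SAP Appendix 2 flags cTnI above 1.0 times the ULN. Provided the LOQ is not above the ULN, neither 0 nor 0.5 × LOQ changes that count. What remains is a question: SAP 5.3 is about missing data, and the SAP does not say whether the sponsor rules give BLQ results a value that the planned geometric mean can use.

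**Conclusion.** The point holds for PD. On its literal wording, SAP 5.3.1 breaks two statistics that SAP 6.2.2 requires, and it gives one sample two values depending on where it appears. The size depends wholly on assumed BLQ frequency and levels: about 1.2 to 4.5 times between dropping and half-LOQ substitution, for 1 to 3 BLQ of 6 and g from 1.5 to 10 LOQ. Exposure is mainly in the concentration-type markers (TFPI, PF1+2, D-dimer). All affected output is descriptive. No hypothesis test is planned, and no primary abnormality count is affected (for cTnI, given the LOQ condition above). For cTnI the finding is only that the applicable BLQ rule needs to be confirmed. The correction is worth making before the data are summarised, so that the choice does not follow the results.

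**What to change.** In SAP 5.3.1:

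1. Limit the zero rule to PK concentration summaries and plots.
2. Apply the SAP's own 0.5 × LOQ value to all PD summary tables, plots and derived parameters. In the illustration above this gives geometric means of 1.89, 1.57 and 1.25 LOQ for 1, 2 and 3 BLQ values. All are finite, use all 6 participants and match the inputs to MaxEff and AUEC.
3. Show the number of BLQ values at each PD time point, as the PK table in effect already does.

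For cTnI, confirm that the sponsor imputation rule cited in SAP 5.3 gives a non-zero BLQ value that the geometric mean in SAP 6.1 can use. Otherwise drop the geometric mean and geometric CV for that test.

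The cost is a few SAP sentences and one extra count in the PD tables, with no new data. The one downside is that, relative to the zero rule, PD arithmetic means rise by 0.5 × LOQ times the BLQ fraction, for example 0.25 LOQ when 3 of 6 are BLQ.

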5.3.2. Deviations, Missing Concentrations and Anomalous Values

In summary tables and plots of mean and median profiles, statistics will be calculated having set concentrations to missing if one of the following cases is true:

- 1. A concentration has been collected as ND (ie not done) or NS (ie no sample).
- 2. A deviation in sampling time is of sufficient concern or a concentration has been flagged anomalous by the pharmacokineticist.

Note that summary statistics will not be presented at a particular time point if more than 50% of the data are missing.

5.3.3. Pharmacokinetic Parameters

Actual PK sampling times will be used in the derivation of PK parameters.

If a PK parameter cannot be derived from a subject's concentration data, the parameter will be coded as NC (ie not calculated). (Note that NC values will not be generated beyond the day that a subject discontinues).

In summary tables, statistics will be calculated by setting NC values to missing; and statistics will be presented with \geq 50% evaluable measurements.

If an individual subject has a known biased estimate of a PK parameter (due to any known error or event related to dosing or sample collection before all the compound is adequately

absorbed in the body), this will be footnoted in summary tables and will not be included in the calculation of summary statistics or statistical analyses.

6. ANALYSES AND SUMMARIES

6.1. Primary Endpoints (Safety Analyses)

All safety analyses will be performed on the safety population (as defined in Section 4).

Analysis of frequency, severity and causal relationship of AEs, TEAEs from Day 1 up to Day 42, and injection site reactions from Day 1 up to Day 7 will be provided. Changes from baseline in vital sign (blood pressure (BP), pulse rate, temperature and respiration rate) measurements and ECG parameters from Day 1 up to Day 28 will be summarized. Physical examination findings from Day 1 up to Day 28 will be listed. Frequency and magnitude of abnormal laboratory findings (including hematology, PT/INR, APTT, chemistry, urinalysis, fibrinogen, ATIII activity, and cTnI), ECG, BP, and pulse rate abnormalities from Day 1 up to Day 28 of potential clinical concern will be described. Safety data will be presented in tabular and/or graphical format and summarized descriptively, where appropriate, according to sponsor reporting standards.

For ECG data, the number of participants with uncorrected QT values >500 msec will be summarized. Listings of subjects with any single postdose value ≥500 msec will also be produced for QTcF. Numbers and percentages of subjects meeting the categorical criteria will be provided. All planned and unplanned measurements will be counted in these categorical summaries. All values meeting the criteria of potential clinical concern will be listed.

Seperate analysis for PT/INR, APTT, fibrinogen, ATIII activity and cTnI will include:

- Descriptive summary including n, mean, median, standard deviation, geometric mean, geometric coefficient of variation (geocv%), minimum, and maximum, will be reported from Day 1 up to Day 28.
- Listing of abnormalities.

Analysis change from baseline for PT/INR, APTT, fibrinogen, ATIII activity and cTnI will include:

• Descriptive summary including n, mean, median, standard deviation, minimum, and maximum, will be reported from Day 1 up to Day 28.

6.2. Secondary Endpoints

6.2.1. Pharmacokinetic Analysis

6.2.1.1. Statistical analyses of PK Parameters

To assess the pharmacokinetics of PF-06741086, the PK parameters detailed in Section 3.2.1 will be listed and summarized for subjects in the PK Parameter Analysis Set (as defined in Section 4). Missing values will be handled as detailed in Section 5.3.

Descriptive summaries of PK parameters will include the set of summary statistics as specified in the table below.

Table 5. PK Parameters to be Summarized Descriptively

Parameter	Summary Statistics	
AUC_{last} , AUC_{inf} , C_{max} , CL/F and V_{z}/F	N, arithmetic mean, median, coefficient of variation (cv%), standard deviation, minimum, maximum, geometric mean and geometric coefficient of variation (geocv%).	
T_{max}	N, median, minimum, maximum.	
t _{1/2}	N, arithmetic mean, median, coefficient of variation (cv%), standard deviation, minimum, maximum.	

There will be 1 summary table presenting all PK parameters.

6.2.1.2. Statistical analyses of PK Concentrations

Analysis for PF-06741086 concentrations from Day 1 up to Day 28 for subjects in the PK concentration analysis set (as defined in Section 4) will include:

- A listing of all concentrations sorted by subject ID, day, nominal time postdose, and actual times. Deviations from the nominal time will be given in a separate listing.
- A summary of concentrations by day and nominal time postdose, where the set of statistics will include n, mean, median, standard deviation, coefficient of variation (cv%), minimum, maximum and the number of concentrations above the lower limit of quantification.
- Median concentrations time plots (on both linear and semilog scales) against nominal time postdose.
- Mean concentrations time plots (on both linear and semilog scales) against nominal time postdose.
- Individual concentration time plots (on both linear and semilog scales) against actual time postdose.

The length of time used for the x-axes of these plots will be decided on review of the data, and will depend on how long PF-06741086 concentration is quantifiable above the limit of quantification in the matrix.

For summary statistics, median and mean plots by sampling time, the nominal PK sampling time will be used, for individual subject plots by time, the actual PK sampling time will be used.

6.2.2. Pharmacodynamic Analysis

The PD parameters from Day 1 up to Day 28 detailed in Section 3.2.2 will be listed and summarized for subjects in the PD Parameter Analysis Set (as defined in Section 4).

Separate analysis for TFPI (total and free), dPT, PF1+2, D-dimer, and thrombin generation (parameters may include lag time, peak thrombin generation, and endogenous thrombin generation potential) for subjects in the PD analysis set (as defined in Section 4) will include:

- Descriptive summaries of PD endpoints by day and nominal time post dose, where the set of statistics will include n, mean, median, standard deviation, geometric mean, geometric coefficient of variation (geocv%), minimum and maximum.
- Median pharmacodynamic endpoint time plots against sampling time.
- Mean pharmacodynamic endpoint time plots against sampling time.
- Individual pharmacodynamic endpoint time plots against sampling time.

Maximum change from baseline and area under effect curve for change from baseline PD values may be summarized if data allow.

Table 6. Other PD Parameters

Parameter	Definition	Method of Determination
Max _{Eff}	Maximum increase and decrease from baseline for free TFPI.	Observed directly from data
	Maximum increase from baseline for total TFPI, PF1+2, D-dimer, endogenous thrombin generation potential.	
	Maximum decrease from baseline for dPT, thrombin generation lag time, peak thrombin generation.	
AUEC	Area under the PD change from baseline-time profile from time zero to Day 28.	Linear/Linear trapezoidal method

The analysis of above parameters for subjects in the PD analysis set (as defined in Section 4) will include:

• Descriptive summary including n, mean, median, standard deviation, coefficient of variation (cv%), minimum, and maximum, will be reported.

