TFPI is a protease inhibitor, which acts as an antagonist of the extrinsic coagulation pathway via inhibition of tissue factor-activated coagulation factor VII (FVIIa) and activated factor X (FXa). TFPI has 2 isoforms, TFPI α and TFPI β. The 2 isoforms share 2 of the same Kunitz type domains (K1 and K2), but TFPI β lacks the K3 domain. Isoforms are distributed in plasma and on vascular endothelial cell surfaces through glycosylphosphatidylinositol anchors. TFPI α is also located in platelets. Available data indicate that a reduced quantity of TFPI in plasma is associated with faster coagulation times and increased thrombin generation. Individuals with TFPI free antigen at the 5th percentile and 2nd percentile have an odds ratio for deep vein thrombosis that is 2.1- and 2.2-fold that of the general population, respectively, indicating a wide therapeutic index is associated with modulation of TFPI activity. These results suggest that TFPI may serve as an acceptable target for a pharmaceutical treatment to reduce inhibition of the extrinsic coagulation pathway and there by increase clotting activity in patients with

bleeding disorders, such as hemophilia.

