### 2.2.1. Nonclinical Pharmacology and Pharmacokinetics

Analysis at the molecular level demonstrated that PF-06741086 targets an epitope in the K2 domain. Surface Plasmon Resonance (SPR) was used to characterize PF-06741086 binding affinity and kinetics of binding to human, cynomolgus monkey, rabbit, mouse, and rat TFPI The neutralization of TFPI by PF-06741086 was measured using a number of in vitro functional assays. The analysis included FXa chromogenic activity assays which measure reversal of TFPI inhibition of Factor Xa or FXa/FVIIa/TF complex in purified systems. PF-06741086 promoted hemostasis in hemophilic plasma from hemophilia A, B, and hemophilia inhibitor plasma and in non-hemophilic plasma as measured in thrombin generation assays (TGA), and dilute prothrombin time (dPT) assays. PF-06741086 inhibitory activity was also demonstrated using thromboelastography (TEG) performed on whole non-hemophilic blood. PF-06741086 also improved the thrombin generation response of severe hemophilia plasma dosed with rFVIIa (eptacog alfa [activated]). The efficacy of PF-06741086 was demonstrated in injury models of hemostasis using Factor VIII deficient mice (model of hemophilia A) and Factor IX deficient mice (model of hemophilia B). PF-06741086 restored hemostasis in hemophilia mouse injury models when administered before and after the onset of a bleeding injury. The pharmacodynamic profile of PF-06741086 is consistent with its TFPI inhibitory activity.

The cumulative pharmacodynamic and potential additive effects of the combined, repeat-dose administration of PF-06741086 and NovoSeven® RT (rFVIIa) was evaluated in rats in a 10-day IV investigative study.

Separate safety pharmacology studies were not conducted with PF-06741086, but safety pharmacology endpoints evaluating the potential effects of PF-06741086 on the respiratory, cardiovascular (CV), and central nervous systems (CNS) were included in the 13-week toxicity study in monkeys.

[figure not shown]

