### 2.2.3.3. Pharmacodynamics of PF-06741086

### 2.2.3.3.1. Following Administration of Single IV or SC Doses in B7841001

Pharmacologic effects reflective of coagulation pathway activation, which includes dPT, prothrombin fragment 1+2 (PF1+2), D-dimer, as well as the TGA parameters of lag time and peak thrombin generation, were monitored in Study B7841001. Total plasma TFPI level was also measured to reflect target binding.

Preliminary PD data following single dose SC administration of PF06741086 at 30, 100, and 300 mg and single dose IV infusion over 1 hour at 150 and 440 mg suggested that treatment related changes were observed for all PD endpoints and generally the response was exposure dependent. Pharmacologic effects on total TFPI as well as a number of PD biomarkers (eg, PF1+2, TGA lag time and thrombin generation, and D-dimer) persist >7 days following administration a single 300 mg SC dose of PF06741086. To support the planned weekly dosing following SC administration, area under the effect curve for change from baseline values (ie, 0H on Day 1) from Days 17 for each PD endpoint was calculated. While changes were observed at all dose levels for some PD endpoints (eg, TGA lag time and TGA thrombin generation), others were only observed at a higher dose level (eg, D-dimer, PF1+2 and dPT at 100 mg and above, and total TFPI at 150 mg and above). Maximum or near maximum effect occurred most frequently following a single dose of 300 mg SC based on these AUC values.

[figure not shown]

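### SAP Table 6 takes the maximum effect on peak thrombin generation as a decrease, although the protocol's pharmacology and the table's own entry for endogenous thrombin generation potential point to an increase

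*SAP*

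**What the plan says.** Protocol Section 9.4.2 defines MaxEff as the maximum pharmacodynamic change from baseline and gives it no direction. The SAP adds directions in Table 6 of Section 6.2.2, in three groups:

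- Both directions: "Maximum increase and decrease from baseline for free TFPI".
- Increase: "Maximum increase from baseline for total TFPI, PF1+2, D-dimer, endogenous thrombin generation potential".
- Decrease: "Maximum decrease from baseline for dPT, thrombin generation lag time, peak thrombin generation".

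The summary is optional: "Maximum change from baseline and area under effect curve for change from baseline PD values may be summarized if data allow".

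On mechanism, Protocol Section 2.2 says that "a reduced quantity of TFPI in plasma is associated with faster coagulation times and increased thrombin generation". Protocol Section 2.2.1 reports for the study drug that "PF-06741086 promoted hemostasis in hemophilic plasma from hemophilia A, B, and hemophilia inhibitor plasma and in non-hemophilic plasma as measured in thrombin generation assays".

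**The concern.** Peak thrombin generation is the only entry on the decrease line that is not a time. An agent that inhibits TFPI should shorten clotting times and raise the amount of thrombin formed, so a decrease is the expected direction for dPT and lag time but not for the peak. Neither document explains why the peak should fall while endogenous thrombin generation potential rises.

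For a marker that rises and then returns towards baseline, the largest decrease is simply the lowest post-dose change. That value comes mainly from samples taken when there is little drug effect, plus measurement error. A reader who took the row at its label could conclude that the drug hardly moved peak thrombin generation, or lowered it slightly.

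**Working it through.** **Step 1. Directions side by side.**

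| Marker | Type of measure | Direction suggested by the protocol | SAP Table 6 |
|---|---|---|---|
| dPT | time | shorter (Section 2.2: faster coagulation) | decrease |
| Lag time | time | shorter (same) | decrease |
| Endogenous thrombin generation potential | amount | higher (Section 2.2: more thrombin generation) | increase |
| Peak thrombin generation | amount | higher (same) | **decrease** |

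Of these four, only the peak disagrees. Sharing an assay with endogenous potential would not settle the matter, because lag time comes from that assay too and rightly carries a decrease. What matters is that the peak and endogenous potential both measure how much thrombin is formed.

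**Step 2. What the rule returns for a marker that rises.** The documents give no effect size, SD or time course for this marker, so there is no plan figure to reproduce. Every effect size, SD and time course below is assumed.

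- Sampling times from the Schedule of Activities, in hours after dosing: 1, 4, 12, 24, 48, 72, then Days 7, 14, 21 and 28 as (day - 1) × 24 = 144, 312, 480 and 648. That makes 10 post-dose samples.
- Shape: s(t) = [exp(-ke·t) - exp(-ka·t)], scaled to 1 at its peak time tp, with ke = ln 2 / half-life and ka solved from tp = ln(ka/ke)/(ka - ke).
- tp = 48, 72 or 108 h; half-life of decline = 33.3, 60, 79.5 or 122 h. The ranges are borrowed from the plasma PK in Protocol Section 2.2.3.2.1, and 60 h is an in-between value.
- Three of the 12 combinations were dropped (72 h with 33.3 h; 108 h with 33.3 h or 60 h), because the resulting curve does not decline with the stated half-life. Nine time courses remain.
- Independent normal error per sample, SD 5, 10 or 20, so 9 × 3 = 27 scenarios per effect size. Baseline error with mean zero does not change the means.
- Observed change at time t = rise × s(t) + error. The expected maximum and minimum over the 10 samples were found by numerical integration.

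| True peak rise | Mean, maximum increase | Mean, rule as written |
|---|---|---|
| 0 | 7.7 to 30.8 | -30.8 to -7.7 |
| 50 | 50.1 to 66.2 | -21.5 to -1.2 |
| 100 | 97.3 to 111.9 | -19.2 to +1.7 |
| 200 | 192.1 to 207.7 | -17.1 to +6.5 |

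At a rise of 100, the rule as written averages -3.7 to +1.7 with SD 5, -8.6 to -2.3 with SD 10, and -19.2 to -12.1 with SD 20.

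**Step 3. Response to the size of the effect.** Doubling the rise from 100 to 200 moves the maximum increase by 92.9 to 99.7 units, close to the full extra 100. It moves the rule as written by only 0.6 to 7.5.

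**Step 4. Effect against noise, like for like.** At a rise of 100, doubling the SD from 5 to 10 moves the rule as written by -3.8 to -4.9. At SD 5, doubling the rise moves it by +0.6 to +4.8. Noise is the larger influence in 7 of the 9 time courses; the two exceptions have a half-life of 122 h with a peak at 48 or 72 h. From SD 10 to 20, noise is the larger influence in all nine.

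**The case against.** **The evidence for a rise is thinner than it first looks.** Protocol Section 2.2.3.3.1 opens a list with "Pharmacologic effects reflective of coagulation pathway activation" and continues "as well as the TGA parameters of lag time and peak thrombin generation, were monitored in Study B7841001". That list also holds dPT and lag time, which are expected to fall, so being on it shows no direction. The downstream effects named in Protocol Section 4.2 mix directions in the same way. The nonclinical statement in Section 2.2.1 is in vitro and names no single assay parameter. Only Section 2.2 gives a direction; it describes an association with the amount of TFPI and does not mention the peak. Parts of the clinical pharmacodynamic results are not visible in the public protocol. All of this stands. The rise is an inference from Section 2.2, supported by Section 2.2.1. The unexplained split between the peak and endogenous potential is still there to read.

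**The illustration is built to give a value near zero.** At 1 h the assumed effect is only about 3 to 7% of its peak, so the minimum must lie close to zero. That is fair. The figures show how the rule behaves under assumed curves and do not predict this trial's data. It also cannot be said that noise always outweighs effect, as Step 4 shows.

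**The practical effect is small.** This also stands. The SAP says the summary and the thrombin generation parameters may be included, not that they will be. No hypothesis is tested, and a rise would show in the by-time summaries, the plots and AUEC.

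**Conclusion.** The concern holds as a minor point. Table 6 gives peak thrombin generation a direction that conflicts with the protocol's account of TFPI and with the table's own entry for endogenous thrombin generation potential, and nothing visible explains it. Confidence in the inconsistency is high. That the peak will rise is a strong inference, not a stated fact.

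If it does rise and the row is produced as written, the row will say almost nothing about the size of the effect and will mislead anyone who reads it as the maximum effect. It would not contradict the time plots. The damage is confined to one optional descriptive row for one component of a secondary endpoint. No primary endpoint or test depends on it.

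**What to change.** In SAP Table 6, do one of two things:

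- move peak thrombin generation to the maximum-increase line, beside endogenous thrombin generation potential; or
- if the sponsor is not sure of the direction, report both the maximum increase and the maximum decrease, as the table does for free TFPI. This needs no view on the direction.

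Leave dPT and lag time as maximum decreases.

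The cost is a one-line SAP correction with no new data. No protocol amendment is needed: Protocol Section 9 and SAP Section 2 call for one only when a primary endpoint's definition or analysis changes in a major way.
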